#### 11.2.1.9. Unscheduled Visit: For AE Follow Up, if Required (3-7 Days after Visit 8)

Investigational center staff will:

- Assess for adverse events including adverse event from device-related skin reaction ongoing at Visit 8
- Update adverse event form or fill in new adverse event form, as applicable.
- An Exit eCRF will be completed at this visit if applicable.

### 12. Assessment of Safety

Adverse Event information is collected in this study. See Section 22 for further information on the collection of AEs and safety information.

### 13. Replacement Sensors

#### 13.1.1. Training Period Sensor Wear Rules

During the training period, if a sensor dislodges prior to completing, the subject may continue with the remaining sensor(s) until the end of the training period.

#### 13.1.2. Study Period Sensor Wear Repeat Rules

A subject can replace their *primary* sensor(s) (See Section 25.8.1) once.

Subject will wear the replaced sensors for 7 days (T=176-188 hours) and attempt to complete the required YSITM\*/SMBG FST visits.

## CIP330 Clinical Investigation Plan 10976639DOC Version D Page 109 of 170 Medtronic

Note: It is important for sites to clearly identify the location of the *primary* sensor so that if it falls out, the site does not confuse the *primary* sensor with a companion sensor that may be located close to the primary sensor.

- For example, if a primary sensor dislodges the subject should replace all sensors and repeat any FSTs not completed.
  - 20 year old subject loses a primary sensor on day 4 and has completed 2 FSTs. Subject should replace all sensors and complete the remaining 2 FSTs. Subject does not have to repeat FSTs already completed.
- For example, if a companion sensor dislodges but the primary sensor is still inserted, the subject should continue with his/her FST schedule.

Scheduling should be performed so that subjects remain in the 90-day window period (i.e. between Visit 1 – Visit 12 for subjects 14-80 years or Visit 1-Visit 8 for subjects 2-13 years).

Subjects will have their YSI™\*/SMBG FST visit rescheduled per the original FST Group.

## 14. Repeat Rules for In-Clinic Procedures

- Concurrent failure of both the primary and back-up YSI™\* instruments during YSI™\* FST.
- If subject experiences unresolved IV occlusions during YSI™\* FST requiring fingerstick measurements for a prolonged time period, the in-clinic procedures may be re-scheduled per sponsor recommendation.
- If primary sensor dislodges and FST cannot be completed. Subject should replace all sensors and repeat any FSTs not completed.

## 15. Medical Oversight

In order to conduct the glucose challenges, staffing with the appropriate training is required:

A physician or mid-level provider, such as a nurse practitioner or a physician assistant, who
has managed diabetic patients must be available during the entire hypoglycemic and
hyperglycemic challenge.

10976639DOC Version D Page 110 of 170

- A nurse, physician or mid–level provider, such as a nurse practitioner or a physician assistant, who has managed diabetic patients must be available during FST.
- The Investigator (or designee) will need to have one of the following qualifications; endocrinology fellowship, management in patients with diabetes in a clinical practice or experience running prior studies performing hypoglycemic induction or rescue. The provider must be qualified to treat diabetic emergencies.
- It is assumed that not every subject who undergo challenge(s) will meet the desired range or desired time per Hyperglycemic and Hypoglycemic Challenge range or time. If a subject is unable to meet the desired range for the desired time for either challenge, the challenge still may be viewed as complete.

## 16. Glucose and Glycemia Measurements

During the course of the study, the subjects' BG, SG levels, HbA1c, blood ketone, and alternate POC BG values will be assessed using the following methods:

- Daily BG- Values will be assessed during the study by all subjects using the CONTOUR® NEXT LINK 2.4 study meter (US only)/ CONTOUR® PLUS study meter (China only). The control solution test will be done following the manufacturer's IFU. Subjects will be trained on the use of the CONTOUR® NEXT LINK 2.4 study meter(US only)/ CONTOUR® PLUS study meter (China only) per the manufacturer's IFU.
- **YSI™\* FST BG values** -During the YSI™\* FSTs at the investigational center, blood plasma glucose will be determined using the laboratory BG analyzer (YSI™\*).
- **SMBG FST BG Values** -During the SMBG FST at the investigational center, the BG will be obtained by SMBG from Study Meter BG readings. Subjects may also use the Study Meter SMBG readings for diabetes management.
- Blood ketone values During the YSI™\*/SMBG FSTs at the investigational center, blood ketones will be determined by subjects using the Precision Xtra™\* ketone meter (US only)/ FreeStyle Optium Neo ketone meter (China only). A QC test will be performed on the meter assigned to each subject before each YSI™\*/SMBG FST. The results of the QC test will be documented in the subject's source documents. The QC test will be done following the manufacturer's IFU. Study staff will be trained on the use of the Precision Xtra™\* (US only)/ FreeStyle Optium Neo ketone meter (China only) ketone meter per the manufacturer's IFU. All blood ketone measurements will be logged in the subject records, and recorded on the appropriate eCRF.
- Sensor Glucose (SG) Values Assessed using the following methods:
  - SG values collected by subject's DS5
- HbA1c Collected at baseline (Visit 1) and will be used as demographic information.
- Alternate POC BG values- During the YSI™\*/SMBG FST at the investigational center, alternate POC BG measurements will be used (CONTOUR® NEXT LINK 2.4 study meter(US)

10976639DOC Version D

Page 111 of 170

Medtronic

only)/ CONTOUR® PLUS study meter (China only)) and the values recorded on the appropriate eCRF (not used for analysis). A QC test will be performed on the CONTOUR® NEXT LINK 2.4 study meter (US only)/ CONTOUR® PLUS study meter (China only) device before each YSITM\*/SMBG FST. The results of the QC test will be documented in the subject's source documents. The QC test will be done following the manufacturer's IFU.

### 17. Recording Data

All data required for analysis will be captured on eCRFs using Oracle Clinical Remote Data Capture's (OC-RDC) module. Original eCRFs will not be considered as source data and supporting documentation will be required. The subject survey on paper is considered source data, then source data is transferred to an eCRF.

**US only**: Blood glucose data will be collected from the CONTOUR® NEXT LINK 2.4 study meter using CareLink™ Personal For Clinical Research software. The system uses Secure Sockets Layers (TLS) technology, which encrypts all data it stores (21 CFR Part 11 compliant).

**China only**: Blood glucose data will be collected from the CONTOUR® PLUS study meter and will be provided to sponsor.

#### **All regions:**

Data from the DS5 will be collected using the Synergy Download Utility Software. Certain data points stored in the downloaded information may also be captured on the appropriate eCRF. These data files will be sent to the sponsor electronically using the internet and a secure cloud-based site (Box).

Electronic data files will be collected from the YSI™\* devices for each subject. These data files will be sent to the sponsor electronically using the internet and a secure cloud-based site (Box).

Laboratory results will be recorded on eCRFs.

The Investigator will ensure that all eCRFs are completed promptly, completely, and accurately. Medtronic will provide detailed instructions to assist with eCRF completion. In the event of data discrepancies, investigational centers will be asked to resolve queries electronically in the OC-RDC system; otherwise, irresolvable data-related issues will be routed to the sponsor for review and final disposition. An audit trail is maintained in OC-RDC to capture any corrections or changes of the eCRFs. System backups for data stored in the Oracle Clinical system will be consistent with Medtronic Standard Operating Procedures (SOPs).

Medtronic will only consider eCRFs to be complete when all discrepancies between source data and eCRF have been resolved and eCRF content has been reviewed by a Study Monitor. In addition, specific eCRFs must also be reviewed and electronically signed by the Investigator, indicating his/her agreement with

## CIP330 Clinical Investigation Plan 10976639DOC Version D Page 112 of 170 Medtronic

the accuracy of all recorded data. It is expected that the Investigator and his/her staff will cooperate with the monitoring team and provide any missing data in a timely manner.

#### 18. Deviation Handling

A deviation is any instance(s) of failure to follow, intentionally or unintentionally, the requirements of the CIP. It is expected that the investigator will conduct this clinical trial in compliance with the CIP and all applicable regulations governing the conduct of clinical research involving human subjects. Failure to do so could result in one or all of the following:

- Investigational center disqualification
- Notification to the regulatory authorities, IRB, or EC depending on the severity of the deviation and reporting requirements

The investigator should not implement any deviation from, or changes to, the CIP without agreement by the sponsor and prior review and documented approval/favorable opinion from the IRB/EC, except where necessary to eliminate an immediate hazard(s) to trial subjects or when the change does not affect the scientific soundness of the plan or the rights, safety, and welfare of the subjects.

The following provides further guidance on what is or what is not a CIP deviation:

Blood glucose range and duration targets

Blood glucose range and duration targets listed for the hypoglycemic and hyperglycemic challenges are targets. It is expected that the investigational centers participating in the study will make their best efforts to reach these targets with the subjects who participate in these challenges, but the sponsor understands that managing diabetes itself is a challenge and meeting these target values and durations for all subjects may not always be possible.

If challenge(s) targets are not met, this will not be considered a deviation.

In the event that samples are not able to be collected or analyzed for technical reasons (YSI™\* or IV line problems) reasons must be recorded on the eCRF and will not be considered deviations.

- FST timing:
  - Out of window protocol deviations related to start of FST time will be given ONLY if the FST is not performed during the scheduled testing day.
- FST Sample:

It is noted that collecting YSIm\*/SMBG FST every 5 – 30 minutes may be challenging. Deviations for missing YSIm\*/SMBG FST samples will only be issued for the following reasons:

- If there are 2 consecutive YSI™\*/SMBG FST samples missing (unless they were missed for safety issues, IV or YSI™\* FST device issues).
  - Example of 2 missing YSI™\*/SMBG FST:

10976639DOC Version D Page 113 of 170

- YSI™\*/SMBG FST at 8 A.M. which is 65 mg/dL (3.6 mmol/L)
- YSI™\*/SMBG FST at 8:15 A.M. which is 60 mg/dL (3.3 mmol/L)

Since the  $1^{st}$  sample is less than (<) 75 mg/dL (4.2 mmol/L), the next draw should be in 5 mins; but the  $2^{nd}$  sample is at 8:15 AM, so there are at least 2 missing samples

- If there are 3 or more total YSI™\*/SMBG FST samples missing per subject per YSI™\*/SMBG FST (unless they were missed for safety issues, IV or YSI™\* FST device issues).
- SMBG:

As subjects may not follow the fingerstick recommendations perfectly, no study deviation will be given unless investigational center staff did not train subject on SMBG study procedures.

#### FST Duration:

A study deviation will not be given if the FST is completed within 15 minutes prior to the 8-hour, 6-hour, and 4-hour duration respectively.

#### 18.1.1. Documenting Requirements for Study Deviations

#### 18.1.1.1. Unplanned CIP Deviations

The investigator may encounter the need to deviate from the CIP when necessary to protect the safety, rights or well-being of a subject in an emergency or in unforeseen situations beyond the investigator's control (e.g. subject failure to attend scheduled follow-up visits, inadvertent loss of data due to computer malfunction, inability to perform required procedures due to subject illness).

Deviations from the CIP, regardless of the reason should be documented as soon as possible, after the deviation occurs or is identified. This documentation should include deviation date, description of the deviation, the reason for deviation, and the corrective action.

CIP deviations should be reported as follows:

- a) To the IRB/EC for notification/acknowledgement;
- b) To the sponsor and, if required;
- c) To the applicable regulatory agency (reported by sponsor)

#### 18.1.1.2. Reporting Requirements for Study Deviations

All study deviations must be reported on the eCRF regardless of whether medically justifiable, an inadvertent occurrence, or taken to protect the subject in an emergency. Any deviations from the CIP will be documented in the clinical study report. The date and reason for each deviation will be documented.

In order to protect the rights and interests, safety and health of subjects, a deviation that occurred under emergency situations that cannot be reported in a timely manner shall be reported in written form afterwards in accordance with relevant regulations as soon as possible.

## CIP330 Clinical Investigation Plan 10976639DOC Version D Page 114 of 170 Medtronic

The following examples are deviations that could impact subject safety, affect the integrity of study data and/or affect subject's willingness to participate in the study. These deviations are significant and require immediate sponsor notification upon investigator awareness:

- Failure to obtain informed consent and assent (if applicable), i.e., there is no documentation of consenting
- Informed consent and assent (if applicable) obtained after initiation of study procedures
- Continuation of a subject who did not meet all inclusion/exclusion criteria
- Performing study procedure not approved by the IRB/EC
- Failure to inform IRB/EC and sponsor of reportable AEs (see Section 22)
- Investigational study device dispensed without obtaining informed consent and assent (if applicable)

Reporting of all other study deviations should comply with:

- IRB/EC policies and/or
- local laws and/or
- regulatory agency requirements

They must be reported to Medtronic as soon as possible upon the center becoming aware of the deviation. Refer to Investigator Reports, Section 27.11.2, for specific deviation reporting requirements and timeframes for reporting to Medtronic, IRB/EC, and regulatory agency (if applicable).

#### 18.1.2. Analyzing Deviations

Medtronic is responsible for reviewing deviations, assessing their significance, and identifying any additional corrective and/or preventive actions (e.g. amend the CIP, conduct additional training, terminate the investigation). Repetitive or serious investigator compliance issues may result in initiation of a corrective action plan with the investigator and investigational center, and in some cases, necessitate suspending enrollment until the problem is resolved or ultimately terminating the investigator's participation in the study.

## 19. Subject Exit, Withdrawal or Discontinuation

Subjects may choose to withdraw from the study at any time by notifying investigational center staff of their intent.

If a subject chooses to end his or her study participation or if a subject is removed from the study at the Investigator's discretion or for failure to meet the study requirements, the reason for withdrawal must be documented. All study devices and supplies must be returned (as applicable) and documented both in source documents and on an eCRF.

Subjects may also be withdrawn from the study at the discretion of the Investigator. A subject may be withdrawn from the study if:

10976639DOC Version D Page 115 of 170

- In the opinion of the Investigator, the subject's health or safety would be compromised by continuing in the study (e.g., infection at skin site, severe skin reaction to adhesive)
- In the opinion of the Investigator, it is in the subject's best interest to discontinue participation in the study
- The subject is found to no longer meet all inclusion criteria, or is found to meet one or more
  exclusion criteria
- The subject fails to comply with one or more study requirements
- The subject is lost to follow up

Documentation of the reason(s) leading to subject withdrawal will be kept in the subject's source documentation.

### 20. Stopping Rules

#### 20.1.1. Stopping Rules for Subjects for FST

- Maximum blood volume drawn:
  - 4 mL/kg (inclusive of all YSI™\* FST days) during this study or 400 cc whichever is more for subjects' age 14-80 years old. However, no more than 3 mL/kg of blood volume in a 24-hour period is to be drawn.
  - 4 mL/kg (inclusive of all YSI™\* FST days) during this study for subjects' age 7-13 years old.
  - o 50 mL will be maximum blood volume for subjects' age 2-6 years old during the study. However, no more than 1 mL/kg of blood volume in a 24-hour period is to be drawn.

Please note that the time of the 24-hour blood draw limit would begin at the start of the first blood draw of an FST and end 24 hours after that. Because patients may have FSTs on two consecutive days (Day 3 and Day 4 or Day 4 and Day 5), please be careful not to exceed the 24-hour blood draw volume maximum. For example, when FSTs occur on two consecutive days it may be preferable to have a hyperglycemic challenge on one day and then a hypoglycemic challenge on the subsequent day, or vice versa, in subjects who may be more likely to reach the maximum 24-hour blood draw volume.

- Severe hypoglycemia (see severe hypoglycemia definition Section 22.1). Subject may continue in study (including observational FST) but not participate in any more challenges.
- Glucose greater than (>) 500 mg/dL (27.8 mmol/L) during challenge. Subject may continue in study (including observational FST) but not participate in any more challenges.
- Ketone greater than or equal (≥) to 3 mmol/L regardless of BG during challenge. Subject may continue in study (including observational FST) but not participate in any more challenges.

# CIP330 Clinical Investigation Plan 10976639DOC Version D Page 116 of 170 Medtronic

#### 20.1.2. Subject Stopping Rules for Study

[figure not shown]
Refer to Section 19 on "Subject Exit, Withdrawal or Discontinuation".

#### 20.1.3. Study Stopping Rules

During a hypoglycemic or hyperglycemic challenge, if a subject experiences DKA, severe hypoglycemia with seizures or severe hypoglycemia requiring glucagon, the following actions will be taken:

- 1. Site will notify the sponsor within approximately 24 hours of receiving knowledge of the event.
- 2. Sponsor will notify Food and Drug Administration (FDA) within approximately 72 hours of knowledge of the event.
- 3. The Clinical Events Committee (CEC) will review the event within 10 days from the time that the sponsor is notified and provide one of the following recommendations:
  - enrollment and study procedures may continue
  - stop enrollment, previously enrolled subjects are still allowed to continue in study
  - stop entire study, withdraw previously enrolled subjects

10976639DOC Version D Page 117 of 170

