#### 9.4. Exclusion Criteria

- 1. Subject will not tolerate tape adhesive in the area of sensor placement as assessed by a qualified individual.
- 2. Subject has any unresolved adverse skin condition in the area of sensor or device placement (e.g., psoriasis, rash, *Staphylococcus* infection).
- 3. Subject is actively participating in an investigational study (e.g., drug or device) wherein he/she has received treatment from an investigational study (drug or device) in the last 2 weeks prior to Visit 1. (Please note participation in an observational study is acceptable.)
- 4. Subject is female of child-bearing potential and result of pregnancy screening test is positive.
- 5. Subject is female of child-bearing potential and who is sexually active should be excluded if she is not using a form of contraception deemed reliable by investigator.

10976639DOC Version D Page 54 of 170

- 6. Subject is female and plans to become pregnant during the course of the study.
- 7. Subject has had a hypoglycemic seizure within the past 6 months prior to enrollment.
- 8. Subject has had hypoglycemia resulting in loss of consciousness within the past 6 months prior to enrollment.
- 9. Subject has had an episode of diabetic ketoacidosis (DKA) within the past 6 months prior to enrollment.
- 10. Subject has a history of a seizure disorder.
- 11. Subject has central nervous system or cardiac disorder resulting in syncope.
- 12. Subject has a history of myocardial infarction, unstable angina, coronary artery bypass surgery, coronary artery stenting, transient ischemic attack (TIA), cerebrovascular accident (CVA), angina, congestive heart failure, ventricular rhythm disturbances or thromboembolic disease
- 13. If subject is 7-80 years of age, subject has a hematocrit (Hct) more than 10% below the lower limit of normal reference range (please note that patients may use prior blood draw from routine care as long as done within 6 months of screening and report of lab placed with subject source documents).
- 14. Subject has a history of adrenal insufficiency.
- 15. Subject is a member of the research staff involved with the study.

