#### **Hypoglycemic and Hyperglycemic Challenges:**

US only: During the YSI™\* FST, subjects with a known insulin sensitivity factor and insulin carbohydrate ratio will undergo hypoglycemic and hyperglycemic challenges.

**China only:** Whether performing recommended challenges or not will be based on EC suggestion and investigator discretion. Absence of challenges during FST will not be considered a protocol deviation.

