#### **Hypoglycemic Treatment Guidelines**

The following are specific hypoglycemic treatment guidelines during the challenges:

Subjects who have glucose less than (<) 70 mg/dL (3.9 mmol/L) and accompanied by seizure, loss of consciousness, or altered mental status (i.e., uncooperative with food or liquid orally so that subject is unable to take carbohydrate to raise glucose) will no longer be allowed to continue in challenges (stop the challenge and DO NOT continue with any future challenges) and the following should be considered:

- Dextrose: 25 grams of dextrose using an ampule (50 ml/25 grams of dextrose) of Dextrose 50% IV push over 3 minutes. Repeat administration may be given again after 15 minutes if glucose is not above 100 mg/dL (5.6 mmol/L). This dose may be adjusted according to investigator discretion based on subject age and other clinical considerations.
- Glucagon emergency kit (glucagon for injection [ribosomal DNA origin] 1 mg, with 1 mL of diluting solution administered intramuscular): may be given if Dextrose was not able to be given due to IV access or per investigator discretion.

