#### Table 3. Investigator Reporting Requirements for AE and Device Deficiencies (China Only)

#### For the following events, reporting requirements are: **Serious Adverse Events (SAE)** Investigators shall immediately adopt appropriate therapeutic measures for subjects, and simultaneously report to the management department of medical device clinical study in investigational center in written form. Management department of medical device clinical study shall report to: Medtronic **Immediately** Within 24 hours Local food and drug regulatory authority and health and family planning competent authority of the province, autonomous region and municipality directly under the central government where the investigational center locates EC Within 24 hours/per EC's requirements For the following events, reporting requirements are: **All other AEs All Device Deficiencies** Investigators shall record all the AEs and device deficiencies occurred during the clinical study. Investigators shall analyze the reasons for the events with Medtronic and document the analysis result in written report, including the comments of continuing, suspending or terminating study, which shall be reported to the EC through management department of medical device clinical study in investigational center for review. To Medtronic Submit in a timely manner

NOTE: In case there is/are additional AE reporting requirement(s) and/or process(es) (e.g. internal hospital policy or province regulatory authority instruction, etc.), these specific AE reporting requirement and process must be documented in a separate cover.

Version D

Medtronic

Page 129 of 170

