#### 27.13.1. Early Investigational Center Suspension or Termination

Sponsor, IRB/EC or a Regulatory Authority may decide to suspend or prematurely terminate an Investigational center (e.g. in case of expiring approval of the reviewing IRB/EC, non-compliance to the CIP or lack of enrollment). The suspended clinical studies cannot be resumed without permission from IRB/EC.

If an Investigational center is suspended or prematurely terminated, Sponsor shall promptly inform the investigator(s) of the termination or suspension and the reason(s) for this. The investigator shall then promptly inform the reviewing IRB/EC and the study subjects.

When the risks are found to outweigh the potential benefits or when there is conclusive proof of definite outcomes, investigators must assess whether to continue, modify or immediately stop the clinical study in the respective Investigational center and immediately inform:

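### Loss of consciousness in a glucose challenge, reversed with IV dextrose alone, would likely not start the timed study-level stopping review, although a seizure reversed the same way would

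*Protocol*

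**What the plan says.** The study-level rule applies during a challenge "if a subject experiences DKA, severe hypoglycemia with seizures or severe hypoglycemia requiring glucagon" (Protocol 20.1.3). The same trigger stands in 23.1 and in the synopsis. It starts three actions: the site tells the sponsor within about 24 hours; the sponsor tells FDA within about 72 hours; and the CEC reviews the event within 10 days of the sponsor being told, then recommends continuing, stopping enrollment, or stopping the study.

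The severe hypoglycemia definition in 22.1 is wider. It needs altered consciousness and active help from another person, and that help may be carbohydrate, glucagon or another resuscitative measure.

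The Hypoglycemic Treatment Guidelines in 10.2.1.6.4.4 cover glucose below 70 mg/dL with "seizure, loss of consciousness, or altered mental status (i.e., uncooperative with food or liquid orally so that subject is unable to take carbohydrate". Any of these ends the subject's challenges. The first rescue listed is IV dextrose, 25 g. Glucagon "may be given if Dextrose was not able to be given due to IV access or per investigator discretion". Section 10.2.1.6.4.6 requires an IV catheter during challenges.

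In the US, "subjects with a known insulin sensitivity factor and insulin carbohydrate ratio will undergo hypoglycemic and hyperglycemic challenges" (10.1). In China, challenges depend on the ethics committee (EC) and the investigator, and their absence is not a deviation.

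**The concern.** For severe hypoglycemia without seizure, the study-level rule turns on which drug was used and not on how ill the subject was. The protocol's own first-listed rescue, given through a line that it requires, keeps a loss of consciousness or coma outside the rule. If the line fails, or the investigator prefers glucagon, the same event may fall inside it.

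This matters because 21.5 gives the challenges, not the device, as the reason for classing the study as significant risk. At US sites, 20.1.3 (with its copies) is the only rule that ties a named clinical event to a required recommendation on whether the study goes on. The stake is whether the next subjects' challenges proceed before anyone has been obliged, by a date, to say that they should. The accuracy analyses are not affected.

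**Working it through.** The plan states no figure to reproduce here, so the check is a comparison of sections followed by a scale calculation.

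**Step 1: does the event trigger 20.1.3?** Take an event during a challenge that meets 22.1, with the presentations of 10.2.1.6.4.4.

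| Presentation | Reversed with IV dextrose alone | Required glucagon |
|---|---|---|
| Seizure | Yes | Yes |
| Loss of consciousness or coma, no seizure | No | Yes |
| Altered mental status only | No | Yes |

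Of 3 presentations, 1 triggers whatever the rescue; 3 − 1 = 2 depend on glucagon.

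**Step 2: which rescue is likely?** Dextrose is listed first, glucagon is a fallback or discretionary, and IV access is mandatory. Dextrose alone is therefore likely. This is an inference from the guideline; the documents give no frequency.

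**Step 3: what do other sections supply for the missed event?**

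- 22.3: all severe hypoglycemia goes to the sponsor, desired within 24 hours. This largely duplicates the first action of 20.1.3.
- 23.1: severe hypoglycemia is on the CEC's general review list, with no deadline and no continue-or-stop recommendation attached.
- 20.1.1: that subject does no more challenges.
- 22.1: the event may be a serious adverse event, if the rescue counts as intervention to prevent life-threatening injury. In the US this gives a second basis for sponsor notice and CEC review. In China, Table 3 then requires immediate sponsor notice and 24-hour notice to the local authority, with EC notice within 24 hours or as the EC requires.
- Table 3, China only: a written report "including the comments of continuing, suspending or terminating study" goes to the EC. That text belongs to the block for other adverse events and device deficiencies, so it may not govern an event classed as serious.
- 22.4: the US expedited duty is for unanticipated adverse device effects. Coma and loss of consciousness are listed challenge risks (21.1), and the sensor only records (7.1.1).
- 27.13 and 27.10: the sponsor may suspend the study or revisit the plan, at its discretion.
- 27.13.1: once risks are found to outweigh benefits, "investigators must assess whether to continue, modify or immediately stop the clinical study in the respective Investigational center". This covers one center and presupposes the finding.

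Of the 3 actions in 20.1.3, 1 is largely covered elsewhere. At US sites, 3 − 1 = 2 are not: the FDA notice, and the CEC review with its deadline and recommendation.

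**Step 4: scale.** Inputs: 100 US and 40 China adult completers, and 20 China completers aged 2–17 (9.1); 2 hypoglycemic challenges per subject (10.1). Assumption: every such subject has insulin ratios and does both.

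- US adults: 100 × 2 = 200.
- China adults: from 0 to 40 × 2 = 80, depending on uptake.
- US share of adult challenges: from 200/(200 + 80) = 71% to 100%.
- The number aged 14–17 is not given. In the split least favorable to the US share (no US and all 20 China pediatric completers aged 14–17, all challenged), it is 200/(200 + 60 × 2) = 62.5%.

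These are planned exposures, not expected events.

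**The case against.** The best defense is deliberate tiering. Section 20.1.1 deals with any severe hypoglycemia at subject level; 20.1.3 is a narrower study-level tier, worded identically in three places and contradicting nothing else. Requiring glucagon could mark failure of the planned rescue, which is a coherent threshold. That explains the glucagon arm. It does not explain why seizure triggers whatever the rescue while coma does not.

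A reader might infer that the protocol treats seizure and loss of consciousness alike throughout and so contradicts itself. The documents do not go that far. The pairing holds for stopping a subject's challenges and for eligibility, where "Subject has had a hypoglycemic seizure within the past 6 months prior to enrollment" and "Subject has had hypoglycemia resulting in loss of consciousness within the past 6 months prior to enrollment" are parallel exclusions. Neither settles study-level escalation, and 22.8 lists seizure separately from severe hypoglycemia as a reportable event. The point is an unexplained difference, not a contradiction.

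It is also fair that rescue is at the investigator's discretion, so which drug would be used cannot be known, and that CEC physicians already see every severe hypoglycemia. Both limit the size of the gap; neither supplies the date, the recommendation or the FDA notice.

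**Conclusion.** The point holds in a limited form. A loss of consciousness or coma in a challenge, reversed with IV dextrose alone, meets 22.1 but would likely not start the FDA notice, the 10-day CEC deadline or the required CEC recommendation. No other section supplies these at US sites. A China site that chose to run challenges would face the same trigger, with stronger local reporting around it.

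A reader might infer that such an event would go unseen or leave the subject unprotected. It would not: the sponsor is told, the CEC reviews it, and that subject's challenges end. What is missing is the timed study-level step.

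Two tempting measures of size should also be set aside. The US share of all completers, 200/260 = 77%, counts children aged 2–13, who do no challenges (11.1). Scaling 200 up by enrolled over completing subjects counts people enrolled at consent (9.2), including screen failures. The 200 planned US adult challenges assume that all have insulin ratios; ages 14–17 and repeated sessions could add to it. With no event rate in the documents, the number of missed escalations cannot be estimated.

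**What to change.** In 20.1.3, 23.1 and the synopsis, redefine the trigger as DKA, or severe hypoglycemia as defined in 22.1 that either involves seizure, loss of consciousness or coma, or requires glucagon. State that altered mental status without loss of consciousness stays at the subject-level tier of 20.1.1 unless glucagon is required. The two tiers then remain distinct.

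Making every use of IV dextrose a trigger is optional and open to debate. It would send nearly all events under 10.2.1.6.4.4 to study-level review and nearly merge the tiers.

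The cost is one phrase in three places, a protocol amendment under 27.10, and possibly a few more FDA notices and 10-day CEC reviews. The CEC already reviews these events, so its added work is the deadline and a stated recommendation.
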